## **9. POTENTIAL RISKS**

The behavioral and physiological assessment procedures employed in these studies are benign. The risks to the study subjects are those related to the administration of the drugs under study. All of the drugs to be administered in the proposed research have been administered safely to human subjects under controlled-laboratory conditions. The relative safety, as well as the contraindications and possible side effects of these compounds are well known and documented. However, the administration of any drug involves some risks simply because individuals differ in their reactions to drugs.

Common side effects of cocaine include anxiety, restlessness, diuresis, irritability, suppressed appetite, insomnia, gastrointestinal upset, increased heart rate, increased blood pressure, palpitations and arrhythmias. It is likely that subjects will experience one or more of these side effects. More serious side effects following the chronic, unsupervised administration of much higher doses of cocaine have occurred and include psychotic episodes, suppressed breathing, seizures, myocardial infarctions, heart failure and death. It is unlikely that subjects will experience these more serious side effects.

Common side effects of amphetamines include nausea, abdominal pain, loss of appetite, dry mouth, weight loss, changes in mood, headache, tremor, difficulty sleeping, nervousness, restlessness, increases in temperature, changes in heart rate or blood pressure (including irregular heart rate and blood pressure), palpitations, anxiety, dizziness, hallucinations, forgetfulness, sleepiness and performance impairment. More serious side effects could include allergic reaction, chest pain, heart attack or other heart related problems, changes in blood platelet levels, stroke, psychotic episodes, seizures, Tourette's Syndrome and sudden unexplained death.

During catheter placement, there is some risk of bruising, soreness, infection, bleeding, pain and irritation from the insertion of the needle. However, these risks are minimal since standard sterile procedures will be used. There is also a risk of syncope. The likelihood of syncope is uncertain and will vary across subjects; however, all medical staff are prepared to manage the occurrence of syncope.

There is also the risk that a subject's PHI may be seen by others. PHI is considered individually identifiable health information transmitted or maintained in any form (electronic means, on paper, or through oral communication) that relates to the past, present or future physical or mental health or conditions of an individual that may be used or disclosed. The following PHI will be collected as part of this project: names (individual, employer, relatives, etc.), address, telephone number, Social Security number, dates (birth, admission, discharge), medical record numbers, driver's license numbers, mental and physical health history, drug use history, results from mental and physical health screening, results from personality questionnaires and data from experimental measures. This risk will be minimized since all appropriate precautions will be taken to protect subjects' PHI, according to the guidelines established by the HIPAA.

The doses to be administered in the present experiment were chosen to minimize, if not eliminate, the chance of these side effects occurring since these side effects are related to dose. Thus, it is unlikely that subjects will experience side effects during the experimental protocol. All experiments proposed in this application will be conducted at the CRU and under medical supervision. Side effects of the drugs are temporary, usually dissipating in less than 24 hours.

There is some theoretical risk that subjects might choose to seek out illicit sources of drugs they received experimentally and liked. However, this risk is minimal since all drugs are administered under blind conditions and in a setting that is not conducive to the development of dependence.

## 10. SAFETY PRECAUTIONS

Protocol management forms will include prompts for research staff members to record any protocol anomalies, data collection problems, concerns with study subjects, or any unusual events that could impact the safety of the subjects or the integrity of the protocol. In addition, the PI, as well as the study physician or his appointed representative, are available at all times by telephone to respond to any questions or concerns that occur during the study. Furthermore, the PI meets with the project staff on a regular basis in the laboratory or by telephone contact to review the study activities.

As described above, Drs. [name], [name] and [name] will screen all potential subjects for physical and psychiatric contraindications to participation. Urine samples will be monitored throughout each study to ensure that female subjects are not pregnant and that all subjects are adhering to the drug use restrictions. All subjects in these studies will be thoroughly informed of the various drug side-effects which they might experience and will be appropriately cautioned concerning their activities in the hours after drug administration. However, this should not pose a significant problem because research subjects will be under the direct supervision of the nursing staff on the CRU at all times during drug dosing. Participation is voluntary, so individuals can withdraw at any time if they find the behavioral procedures or drug effects undesirable. The drug doses to be administered in the present experiments were chosen to minimize, if not eliminate, the chance of these side effects occurring. As noted above, Drs. [name], [name] and [name] will screen all potential research subjects for medical contraindications, and [name] will review the ECG, prior to study participation. Drs. [name], [name] and [name] will monitor research subjects throughout their participation. We anticipate that careful subject selection, dose selection and subject monitoring will greatly reduce, if not eliminate, the occurrence of serious side effects. The assembled team of investigators has been conducting inpatient and outpatient human behavioral pharmacology studies with healthy subjects and subjects with histories of drug abuse for more than 60 years combined and have never observed a serious drug-related unanticipated serious adverse event. To monitor for adverse events/side effects, the Udvalg for Kliniske Undersøgelser (UKU) Side Effects Rating Scale will be completed daily with subjects by CRU nursing staff. Staff observations, subjective-effects drug effects and spontaneous subject report will also be used to monitor for adverse events.

To minimize the risk associated with intravenous cocaine administration, dosing will occur under the supervision of ACLS-certified medical staff ([name] and CRU nurses). During the medical safety and experimental sessions, heart rate and blood pressure will be recorded prior to cocaine administration and at frequent intervals (i.e., every 2 minutes) afterwards for the duration of the session. Prior to cocaine administration, subjects must have a heart rate of  $< 130$  bpm, systolic blood pressure  $< 165$  mm Hg and diastolic blood pressure  $< 100$  mm Hg. Heart rhythmicity will be recorded continuously via 3-lead telemetry during each experimental session, and will be monitored continuously for a minimum of 15 minutes following each infusion. Subjects who exhibit hypersensitivity (i.e., HR and BP outside of parameters or abnormal ECG) to the cardiovascular effects of cocaine at any point during these studies will not receive further doses, will be followed until symptom resolution, and will be excluded from further research participation. Cardiovascular hypersensitivity is defined as heart rate  $> (220 - \text{subject age}) \times 0.85$ , systolic pressure  $> 180$  mm Hg or diastolic pressure  $> 120$  mm Hg elevated consistently across a five minute period of monitoring (see above). Cardiovascular hypersensitivity also includes prolonged abnormal heart rhythmicity, which is defined as ventricular arrhythmias that occur at a frequency greater than 5 per minute, are multifocal, or occur as couplets

(2 consecutive beats) or salvos (3 or more consecutive beats), and persist for greater than 15 min. Ischemia or other abnormalities as described in the exclusion criteria would also be cause for discharge. A cardiovascular emergency will be managed using UK medical center procedures (i.e., response from a code blue team).

Subjects will be required to report a history of cocaine use via the smoked or intravenous route to be eligible for study participation. Therefore, subjects who do not have a history of intravenous cocaine use (i.e., those individuals reporting smoked cocaine) will likely be enrolled and receive cocaine by a new route of administration. The National Advisory Council on Drug Abuse guidelines indicate that “a thorough assessment of the risks entailed if participants are to be exposed to...a new route of administration than they would normally encounter by their own choice in their usual circumstance.” We do not feel that the administration of intravenous cocaine to subjects who report no previous experience by this route of administration puts subjects at undue risk for two reasons. First, smoked cocaine administration results in a rapid onset and greater self-reported effects compared to intravenous cocaine at doses that produce comparable blood concentrations, and smoked cocaine was chosen over intravenous cocaine in a self-administration procedure, suggesting that the abuse potential of intravenous cocaine is less than smoked cocaine (Cone, 1995; Foltin and Fischman, 1991, 1992). Second, a study that evaluated cocaine use patterns following investigational intravenous cocaine administration to intravenous-naïve cocaine users did not detect changes in frequency of illicit cocaine use or the adoption of intravenous use after study participation (Kaufman et al. 2000). Furthermore, several investigative teams have published studies in which intravenous cocaine was administered to human subjects with a history of smoked, but not intravenous, cocaine (e.g., Haney et al., 1998; Newton et al., 2001; Walsh et al., 2010), demonstrating that the field finds this practice acceptable from an ethical standpoint. Also worth noting is that some subjects who have participated in our previous research have reported intravenous cocaine use.

Subjects will receive intravenous cocaine during maintenance on oral d-amphetamine, which could further increase the risk for adverse cardiovascular events. However, previous clinical research has demonstrated the safety and tolerability of cocaine administration during d-amphetamine maintenance, suggesting that cardiovascular risk in the proposed studies will be minimal. In a study by Greenwald and colleagues (2010), subjects were maintained on d-amphetamine SR at the doses proposed in this application (i.e., 30 and 60 mg/day). d-Amphetamine modestly, but significantly, elevated baseline heart rate and systolic and diastolic blood pressure readings (an increase of approximately 10 bpm, 12 mmHg and 10 mmHg, respectively); however, a bolus dose of 100 mg intranasal cocaine failed to further increase these cardiovascular parameters. In our previous study in which we administered up to 60 mg of intranasal cocaine during maintenance on 30 mg/day d-amphetamine, baseline heart rate and systolic blood pressure were elevated (approximately 6 bpm and 5 mmHg, respectively) and then further increased by cocaine ([name] et al., 2009). However, maximum heart rate did not exceed 95 bpm or 130 mmHg on average following cocaine administration, and no adverse cardiovascular events occurred. In a second study, up to 30 mg of intranasal cocaine was administered during maintenance on 40 mg/day d-amphetamine ([name] et al., 2010). In that study, cocaine significantly increased systolic and diastolic blood pressure, and d-amphetamine maintenance further increased BP, but only by a maximum of about 5 mmHg, and not to a statistically significant degree. Lastly, a review by Herin and colleagues (2010) evaluated the risk profile of d-amphetamine maintenance on an outpatient basis in treatment seekers and found it favorable. The results of several controlled clinical trials incorporating careful monitoring of side effects, including frequently repeated ECGs, indicated that the effects of d-amphetamine maintenance on blood pressure and heart rate were nominal. Similarly, multiple reports from community-based clinics failed to note serious adverse events in diverse populations.

As noted above, serious side effects of stimulants include seizures. The occurrence of seizures appears to be related to the presence of certain predisposing factors including histories of head trauma, seizures or CNS tumors and the administration of concomitant medications that lower seizure threshold. Subjects that report personal histories of head trauma, seizures or CNS tumors or a first-degree family history of seizures will be excluded from research participation. Most seizures resolve of their own accord and typically, individuals with a history of seizures will be the only ones who require intervention. In the event that a seizure should occur, the standard response is to allow 15 minutes for it to spontaneously resolve. If the seizure has not stopped within the allotted time, diazepam is to be administered by the attending physician or his designee. Because we

exclude individuals with a history or risk of seizures, it is very unlikely that a subject will have a seizure or that we will need to administer diazepam. If a research subject experiences a seizure he/she will be excluded from further research participation.

Potential subjects must meet criteria for cocaine-use disorders to be enrolled in the proposed experiments. It is possible that these subjects will experience abstinence symptoms once admitted to the CRU. As noted above, we have several safeguards in place to monitor for adverse events. If a subject experiences significant symptoms of abstinence following admission to the CRU, he or she will be treated in accordance with the standard practice of the University of Kentucky Hospital and then dismissed from the study.

To avoid potential drug interactions, volunteers taking any prescribed medication chronically, except birth control, will be excluded. The medical personnel on this protocol will determine if it is safe for a potential volunteer to discontinue taking their medication during their participation.

All subject PHI is confidential and will be protected according to the guidelines established by the HIPAA. An "Authorization to use and disclose PHI for research purposes" approved by the UK IRB will be obtained. This allows the investigators on this project to use or share health information with the United States Department of Health and Human Services (DHHS) representatives, the UK IRB, the UK Office of Research Integrity (ORI), UK medical center representatives, other research collaborators or when required by law. In addition, a Certificate of Confidentiality will be obtained from NIDA. All PHI will be protected as described above for safeguarding experimental data and PHI in the Research Materials section.

During the course of participation in the research, a subject could experience dissatisfaction or discomfort with the experimental procedures. A research staff member will be immediately available to address these issues, and the study subjects have telephone contact information to reach both the PI and the study physician. In addition, if individuals become overly distressed or distraught, participation in the study is discontinued immediately and private consultation with the study physician and/or PI is offered immediately.

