### *Inclusion Criteria:*

- Recent cocaine use via the smoked or intravenous route, verified by a cocaine-positive urine sample.
- Otherwise healthy, without contraindications to cocaine.
- Meet Cocaine Dependence or Abuse criteria, verified by Structured Clinical Interview for DSM-IV (SCID).

-Use of an effective form of birth control (e.g., birth control pills, surgical sterilization, IUD, cervical cap with a spermicide, condoms or abstinence; females only). A urine pregnancy test will be conducted before the start of each session to ensure that female subjects do not continue in the study if pregnant.

*Exclusion Criteria:*

- Chemistry values or screening outcomes including outside normal ranges that are deemed by the study physician to be clinically significant. Lipid levels, which have not typically been included in our screening tests, are included in this protocol as an additional check for cardiovascular health.
- Hypertension  $\geq 140/90$  mmHg during screening or before dosing on the medical safety session
- BMI  $\geq 30$ .
- Electrocardiogram abnormalities, including:
  - Atrial premature beats ( $\geq 2$  consecutive)
  - Ventricular premature beats (Lown's Grade 3 or higher;  $\geq 2$  consecutive beats, multiform)
  - Heartblock (2nd or 3rd degree AV block or bundle branch block)
  - Pre-excitation syndromes (Wolff-Parkinson-White or Lown-Ganong-Levine)
- History of serious physical disease, current physical disease, impaired cardiovascular functioning, chronic obstructive pulmonary disease, history of seizure, or current or past histories of serious psychiatric disorder that in the opinion of the study physician would interfere with study participation.
- First degree family member with significant premature cardiac comorbidity.
- Current or past histories of substance abuse or dependence that are deemed by the study physician to interfere with study completion.

Screening procedures for all subjects will include a medical history questionnaire, laboratory chemistries (blood chemistry screen, complete blood count, ECG and urinalysis) and a brief psychiatric examination. These procedures will be conducted under our lab's screening protocol (03-0509). All study participants will be judged by the study physicians, Drs. [name], [name], [name], or their representative, to be healthy.

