8-11	Self-administration sessions. Subjects complete 1 sample and 9 choice trials to receive cocaine (0, 3, 10 and 30 mg/70 kg) or money (\$6.00) by responding on the concurrent PR schedule.
12-20	d-Amphetamine SR maintenance (placebo; 0 mg administered twice daily).
17-20	Self-administration sessions. Details are the same as Days 10-13.
21-29	d-Amphetamine SR maintenance (60 mg daily). Oral dose administered twice daily (0700 and 1900 h) in escalating fashion up to target daily dose (i.e., doses 1-3 = 5 mg, doses 4&5 = 10 mg, doses 6&7 = 20 mg, remaining doses = 30 mg).
26-29	Self-administration sessions. Details are the same as Days 10-13.
30	Discharge from the CRU.

During their participation in the research protocol, volunteers will not be allowed to leave the CRU, nor will visitors be allowed. Research volunteers will be allowed to make local telephone calls. After completing the

research protocol, interested volunteers will be offered a referral to an appropriate drug abuse treatment program.

All volunteers will provide urine and expired air samples daily during study participation once experimental sessions have been initiated. The presence of non-nicotine, non-cannabinoid drugs of abuse or alcohol not administered experimentally in the research protocol will result in immediate termination from the research study.

This experiment will consist of 12 experimental sessions across approximately 33 days and conducted according to the timeline in Table 1 (see above). On the day of admission, volunteers will be allowed to acclimate to the CRU. During this time, volunteers will be maintained on a caffeine-free diet, receive instructions concerning the details of the daily research procedures and general rules of the inpatient research unit and complete a "practice" session to familiarize them with the experimental routine and tasks. The practice session will follow the session timeline with the exception that no drug or response-contingent money will be available and no maintenance dose will be administered. On the day after the practice session, subjects will participate in a medical safety session in which they will receive each of the doses IV cocaine that will be available in subsequent sessions (i.e., 1 infusion of 0, 3, 10 and 30 mg/70kg cocaine) administered in ascending order and separated by 30-min intervals; subjects exceeding the predetermined cardiovascular parameters will be excluded from further participation.

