Cardiovascular hypersensitivity is defined as heart rate  $> (220 - \text{subject age}) \times 0.85$ , systolic pressure  $> 180$  mm Hg or diastolic pressure  $> 120$  mm Hg. ECG. If vital signs are elevated above these criteria, the nurse or physician will re-assess using the automated machine at minute intervals for 5 total readings. If vital signs remain above these criteria for all 5 readings, a manual reading will be taken. If vital signs are still elevated, a subject will not receive further doses, will be followed until symptom resolution, and will be excluded from further research participation. These criteria have been recommended by [name]., who served as an advisor in the preparation of this protocol, and used in previous studies of intravenous cocaine self-administration in humans (e.g., Walsh et al., 2010). Cardiovascular hypersensitivity also includes prolonged abnormal heart rhythmicity assessed via 3-lead telemetry. Abnormal heart rhythmicity during experimental sessions is defined as ventricular arrhythmias that occur at a frequency greater than 5 per minute, are multifocal, or occur as couplets (2 consecutive beats) or salvos (3 or more consecutive beats), and persist for greater than 15 min. A cardiovascular emergency will be managed using UK medical center procedures (i.e., response from a code blue team). In [name] previous study at the CRU that guided the medical safety monitoring parameters for the present protocol, subjects were administered up to 320 mg/70 kg intravenous cocaine across an experimental session (i.e., maximum of 8 administrations of 40 mg/70 kg). Important to note is that none of the subjects (N=22) were discharged due to exceeding the cardiovascular threshold criteria. One subject experienced premature ventricular contraction after receiving placebo and active cocaine, and was subsequently discharged. Cocaine produced expected increases in heart rate and blood pressure, but there were no clinically significant changes that required cessation of cocaine dosing or protocol discharge. Likewise, no subjects have been discharged from the ongoing protocol in which subjects self-administer various doses of IV cocaine (0, 3, 10 and 30 mg/70 kg) due to cardiovascular adverse events.

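### Section 10 gives two rhythm discharge rules that disagree for ventricular couplets and salvos lasting 15 minutes or less, and Section 7 carries only one of them

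*Protocol*

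**What the plan says.** Three places in the Protocol bear on when an abnormal rhythm ends a subject's participation.

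- **Section 7 (Research Procedures)** counts prolonged abnormal rhythm as cardiovascular hypersensitivity. It covers ventricular arrhythmias that exceed 5 per minute, or that "are multifocal, or occur as couplets (2 consecutive beats) or salvos (3 or more consecutive beats), and persist for greater than 15 min".
- **Section 10 (Safety Precautions)** opens broadly, with "Subjects who exhibit hypersensitivity (i.e., HR and BP outside of parameters or abnormal ECG) to the cardiovascular effects of cocaine at any point", and provides that such subjects get no further doses and are excluded. It then repeats the Section 7 rhythm definition, ending "2 consecutive beats) or salvos (3 or more consecutive beats), and persist for greater than 15 min". The sentence directly after that reads: "Ischemia or other abnormalities as described in the exclusion criteria would also be cause for discharge".
- **Section 4 (Exclusion Criteria)** lists, among the electrocardiogram abnormalities, "Ventricular premature beats (Lown's Grade 3 or higher", with the detail of two or more "consecutive beats, multiform". No minimum duration is attached. The other items in the list are atrial premature beats, heart block (including bundle branch block) and pre-excitation syndromes.

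**The concern.** By itself the Section 4 list decides only who may enroll. The cross-reference in Section 10 turns it into a list of discharge grounds during treatment. One item on it, consecutive ventricular beats, is the pattern that the preceding sentence of Section 10 has just made subject to a 15-minute persistence condition. The same event is then judged by two rules, one with a duration and one without. Staff who work from the procedures in Section 7 see only the rule with a duration.

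At stake is whether intravenous cocaine may be given again, during d-amphetamine maintenance, to a subject who has just had a brief run of consecutive ventricular beats. Section 10 itself acknowledges that the combination could raise cardiovascular risk further. Two clinicians acting in good faith could decide the same case differently.

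**Working it through.** There is no planned figure to reproduce. The check sets the rules side by side and applies them to the same event.

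**Inputs**
1. Rhythm definition, Sections 7 and 10: couplets are 2 consecutive beats, salvos are 3 or more, and duration must exceed 15 minutes. The duration is taken to apply to every listed pattern, which fits the word *prolonged* that introduces the definition in both sections.
2. Added ground, Section 10 only: ischemia or the abnormalities in the exclusion criteria, no duration.
3. Ventricular item, Section 4: 2 or more consecutive beats, multiform, no duration.

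**Does the Section 4 item cover the Section 10 patterns?** A couplet has 2 consecutive beats and a salvo has at least 3, so both satisfy *2 or more*. The comma before *multiform* can be read two ways:
- Read as *or*, every couplet and salvo is covered. So are multifocal beats, provided that *multiform* (Section 4) and *multifocal* (Sections 7 and 10) mean the same.
- Read as *and*, only multiform couplets and salvos are covered. The overlap shrinks but does not disappear.

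**Applying the rules to a run of couplets or salvos (comma read as *or*)**

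| Rule | Lasts 10 min | Lasts 20 min |
|---|---|---|
| Section 7 definition (more than 15 min) | not met | met |
| Section 10 definition (more than 15 min) | not met | met |
| Section 10 added sentence, through Section 4 (no duration) | met | met |

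The rules agree above 15 minutes and part at 15 minutes or less. The first point of disagreement is therefore inside Section 10, between two adjacent sentences. The difference from Section 7 follows because Section 7 lacks the second sentence.

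**Do other provisions settle a short episode?** Choice trials are 30 minutes apart. An episode of at most 15 minutes that starts within the first 15 minutes after an infusion is over by minute 15 + 15 = 30. The pre-dose check that rhythm is normal can then be passed. Section 7 also has the ECG read 15 minutes after each infusion and tells nurses to contact physicians about abnormalities. Section 10 keeps a physician reachable at all times, and Section 17 lets investigators withdraw a subject for safety. These provisions get the episode seen and referred. None says which of the two rules the physician should apply once it has resolved.

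**The case against.** The best counter-argument is that the sentence has a natural reading without conflict. It follows a full definition of ventricular arrhythmia and speaks of *other* abnormalities that would *also* count. Those could be ischemia and the non-ventricular items of Section 4, which would leave the 15-minute rule intact. A second reading makes two tiers: hypersensitivity excludes the subject outright, while *cause for discharge* leaves room for judgement. The account of the guiding study in Section 7 fits that. None of 22 subjects was discharged for exceeding the threshold criteria, yet one with premature ventricular contraction was discharged; the duration and pattern are not given.

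Both readings are possible, and they are why this is an inconsistency to clear up and not proof that the investigators intend the wrong rule. Neither is stated. The cross-reference points to the exclusion criteria without setting any item aside, and *other* follows directly on ischemia. A stopping rule should not depend on an exception that the reader has to supply.

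Two stronger inferences are not supported:
- A reader might infer that Section 7 directs staff to keep dosing a subject after a brief episode. It does not. It is silent below the threshold, and it shares that threshold with Section 10.
- A reader might try to size the problem by the cocaine still available later in the session. That requires the rhythm to be verified normal before every later dose, cocaine to be chosen every time, and no contacted physician to intervene. The documents give no basis for assuming this chain of events.

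**Conclusion.** The rhythm discharge rule in Section 10 is internally inconsistent. Taken literally, its cross-reference to Section 4 cancels the 15-minute condition for couplets and salvos, and Section 7 repeats the condition without the cross-reference. The conclusion assumes that *other abnormalities* includes the ventricular item of Section 4. How far it reaches depends on the comma and on whether *multiform* equals *multifocal*.

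The affected events are episodes of 15 minutes or less. The documents give no rate for them in this design. Section 7 suggests that cardiovascular discharges are uncommon: besides the guiding study, it reports that "no subjects have been discharged from the ongoing protocol in which subjects self-administer various doses of IV cocaine" for cardiovascular adverse events, at the same cocaine doses, though d-amphetamine is not mentioned there. No endpoint, sample size or analysis figure changes. This is a wording defect in a safety rule. It should be corrected because the correction is cheap and the rule governs repeat dosing with cocaine.

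**What to change.** State one rule, in the same words, in Sections 7 and 10.

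- **Default (safer, and follows the literal text):** couplets or salvos meeting the Section 4 criterion after cocaine stop dosing and are cause for discharge regardless of duration. The condition of more than 15 minutes stays for other ventricular ectopy above 5 per minute. Repeat in Section 7 the sentence on ischemia and the exclusion-criteria abnormalities.
- **Alternative:** if the study physicians intend persistence to govern all ventricular ectopy, limit the Section 10 cross-reference to ischemia and the non-ventricular items of Section 4, and say so in both sections.

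Under either choice, use one term (multiform or multifocal) in Sections 4, 7 and 10. Replace the comma in Section 4 by *and* or *or*, so that it is clear on which side multifocal beats fall.

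The cost is amendment wording in two sections, a small edit in Section 4 and an instruction to the nurses. No equipment, staff or visits are added. The downside of the default is that a few subjects with brief ectopy may be discharged and need replacing.
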